## 5.5 Study Evaluations

The table below lists which measures are collected from participants at each time point in the study. Data is recorded by the research assistant into secure study tracking SQL database or RedCap. The study team will develop an acceptable standardized time window for data collection around each timepoint.

Study visits/interactions:

Aim 1: Formative Evaluation

Qualitative Interview	x	
Adaptation Virtual meeting	x	
Revision Qualitative Interview	x	
Aim 2: Intervention	Intervention	Usual Care
Enrollment Visit (baseline measurements)	x	x
Intervention Call – 1 week after enrollment visit with Interventionist	x	
Follow-up Intervention Call – 2, 4, 6, 8, 10,12 month after first call with Interventionist	x	
Adhoc check in call/video visits for BP/Statin med adjustments	x	
4, 8, 12 month outcome measurements –in person visit* with RA (to include measuring height, weight, BP, waist, and lipid panel at lab)	x	x
Aim 3: Process Evaluation Feedback on the intervention collected by phone.	x	
Note: * if in-person study visits are discontinued for reasons out of our control or for pandemic closure we will convert them to VVC visits to capture BP outcome and schedule participants for labs with 4 weeks of BP collection. We will accept clinical labs for same lab if they have been collected within time frame.		

Patient surveys for each time point are attached at the end of this document.

Data element	Source(s)	Time period
Aim 1: Formative Evaluation		
Perceptions of the self-management for CVD, HIV. Lifestyle change and medication adherence.	Audio recordings and field notes from qualitative interviews	Aim 1:
Aim 2: Intervention/ Survey		
Chart Abstraction/Review and screening	Site CPRS medical records/CDW	Pre enrollment
Hypertension diagnosis	Site CPRS medical records/CDW	0, 12
HIV + diagnosis, HIV history (prior labs, treatment and appointments), recent hospitalizations and ED visits, MOVE program participation	Site CPRS medical records/CDW	0
Demographics, family history of CVD, health literacy, prior home BP use, technology use, life chaos, loneliness, pain, housing and food insecurity, financial strain, anxiety and depression, physical function	Self-reported survey responses	0
Medications, comorbidities, labs, alcohol use	Site CPRS medical records/CDW	0, 4, 8, 12
Health behaviors such as physical activity, diet, tobacco use, medication adherence, sleep, stress,	Self-reported survey responses	0, 12

Data element	Source(s)	Time period
alcohol and substance use		
Aim 3: Qualitative Interviews		
Perceptions of CVD risk, self-management strategies and barriers, and intervention delivery strategy. For example, we will ask participants which aspects of the intervention were most and least helpful, appropriateness of the number and length of telephone sessions, and ways we may be able to further improve the intervention.	Audio recordings and field notes from semi-structured interviews	12
Optional sustainability interviews: 6-12 months after completing intervention, to hear participants' long-term perspectives from completing the study and developing a better understanding of the sustainability of the intervention	Audio recordings and field notes from semi-structured interviews	18 - 24 months
Exploratory Aim: Cost Impact Analysis		
Hospitalizations, Labor & Capital cost	CDW/Self-reported data	0, 12

## 5.6 Data Analysis

**Aim 1: Formative Evaluation.** Data will be analyzed by the Qualitative team in collaboration with PI.

**Analysis for Aim 1a:** Quantitative data (e.g., medical history, perceptions of CVD risk) will be summarized and used to describe study samples. After redacting all identifying information, verbatim transcriptions of recorded interviews will be entered into NVivo 12. A quality assurance protocol for qualitative analysis will be built into data management and analysis; 25% of the transcripts will be checked to verify accuracy of the transcriptions and 10% will be double-coded to ensure inter-coder reliability of 80% or greater.

All responses will be analyzed using standard thematic analytic techniques for qualitative data: identification of themes/domains; coding or classification of participants' responses by these themes performed independently by two team members; resolution of any coding discrepancies will be done by a third team member. To ensure consistency, a codebook and dictionary will be developed to create universal definitions for each code. The architecture of the interview guide domains - informed by our theoretical lens of RE-AIM, Self-Regulatory Theory, and the Information-Motivation-Behavioral skills model - will drive the initial coding of our data. Yet, significant inductive (emerging) codes will also be identified. Coded items will be grouped together into distinct themes. Finally, the analytic team will work from the coded data to merge findings into a report of findings to aid in the intervention development. Key findings will be abstracted into a matrix and mapped to existing intervention components to aid integration and map adaptation to inform participatory, iterative design process in Aim 1b. This method of data reduction encompassing a multidisciplinary team-based analysis creates a robust iterative process through which the data are thoroughly discussed and analytical consensus achieved. Findings from these interviews will be presented back to the study team and site leadership to inform context-specific adaptation of the intervention.

**Analysis for Aim 1b:** We will use a participatory, iterative design process as the analytic approach for Aim 1b. The results will be a documentation of key adaptations of the evidence-based practices to inform intervention redesign to optimize clinical impacts and feasibility and acceptability of innovation uptake.

**During brainstorming**, the team will review the data obtained during the baseline assessment on perceptions of ASCVD risk and barriers and facilitators of ASCVD preventive care obtained during Aim 1a. The team will brainstorm ideas to refine the intervention in response to these data. Ideas will be captured in a structured, written format for the next phase.

**In the conceptualization phase**, the team will evaluate advantages and disadvantages of ideas generated during the brainstorming phase, and will develop concrete changes (ie., adaptations) to the intervention. For example, if the team decides to include the name of the provider (PCP or HIV specialist) responsible for BP and lipid management in the intervention program, we will discuss its feasibility. All final adaptations will be captured in a structured, written form to aid in implementation in the revision phase.

**The creation and revision phases** will involve the refinement of treatment protocols, manuals of procedures, and educational materials. Once the adaptation of the intervention is completed, we will present the adapted model to our Veteran Engagement Quorum and up to 9 intervention staff from each of the three sites to assess acceptability. We will document any further adaptations resulting from these engagements in a structured written format to be implemented into the treatment protocols, manuals of procedures, and educational materials.

We will also analyze the perspectives from design team members in the final meeting about their experience participating in the Human Centered Design process. Content analysis of individual surveys and group discussions will be performed by the qualitative staff members and coded based on emergent themes captured. Core outcomes of interest for the surveys and discussions will include: a) previous design team experience; b) comprehension of the design team experience; c) thoughts on the design team process for the intervention; d) reflections on each phase of the human-centered design approach; and e) perceptions of the final intervention model.

#### **Analysis for Aim 1c:**

We will describe the HTN care cascade among PWH over a period of 5 years based on data definitions described above. To estimate proportions along each cascade, we will conduct descriptive analyses and obtain frequencies and percentages of Veterans at each previously defined step compared with the preceding step. We will conduct univariate analyses to describe demographic and baseline characteristics of the cohort. Means and SDs will be obtained for continuous variables, whereas percentages and frequencies will be used to describe categorical variables. We will stratify the data into 2 subpopulations: HIV and HIV/HTN and compare baseline characteristics of these 2 subgroups.

**Aim 2: intervention.** Data will be analyzed by PhD & Master Statistician in collaboration with PI

**Analysis:** The primary outcome will be systolic BP at 12 months and secondary outcome will be non-HDL cholesterol at 12 months, both measured at 4 time-points (0, 4, 8, and 12 months). All BPs used for outcomes will be obtained by a research assistant and cholesterol levels will be measured by lab personnel who are also blinded to treatment group. Because the outcomes are continuous, linear mixed-effects models (LMM) will be used to examine the differences over time between the study arms. LMM will allow us to implicitly account for the correlation between a patient's repeated measurements over time. The general mean structure of the LMM we will use to examine the hypotheses

$$Y_{ij} = \beta_0 + \beta_1 * I(month = 4) + \beta_2 * I(month = 8) + \beta_3 * I(month = 12) + \beta_5 * arm * I(month = 4) + \beta_6 * arm * I(month = 8) + \beta_7 * arm * I(month = 12),$$

where  $Y_{ij}$  represents the outcome of interest (i.e., SBP or non-HDL) for patient  $i$  at time  $j$ . We will fit a common intercept and arm is the intervention group indicator. Similarly, time will be classified, where for example,  $I(month = 12)$  is a dummy variable equal to 1 for the 12 month time point. Random intercepts will be included for each individual to account for correlation among repeated measurements over time. The primary analytic model will adjust for clinic site and hyperlipidemia status. The mixed effects model parameters will be estimated and tested using SAS PROC MIXED (SAS Institute, Cary, NC), and the hypothesis of between-arm differences over time will be tested using estimate statements within PROC MIXED. In particular,  $\beta_7$ , the estimated difference in outcome between arms at 12 months, will be the primary effectiveness outcome

assessed. All analyses will be conducted following an intention to treat (ITT) principle.

**Missing data.** We will assess mechanisms for missing data in this study. LMM, implicitly accommodates missingness when the response is Missing At Random (MAR); that is, when missingness is due either to treatment, to prior outcome, or to other baseline covariates included in the LMM.

Our primary analysis will include all available study-collected data. A sensitivity analysis will be conducted by filling in missing data in the following manner:

1. Use all available study-reported data.
2. If missing study-reported value → use the SBP or non-HDL cholesterol value if available in the EMR in a 2 month window from the target data for that time point
3. If missing EMR-reported value → assess whether the outcome has >10% missing remaining.
  - a. If yes, ≥10% missing → use multiple imputation
  - b. If no, <10% missing → do not use multiple imputation, include only study- and EMR-reported values

The final determination whether to use multiple imputation is separate for SBP and non-HDL cholesterol outcomes; SBP could meet the criteria and non-HDL does not, or vice versa.

If multiple imputation is indicated, we will use multiple imputation procedures as described by Schafer. Once missing values have been imputed, each multiply-imputed data set can be analyzed using the LMM. Final parameter estimates and their standard errors will be calculated using Rubin's formula.

We will analyze our data and report final study results and carefully examine and describe any discrepancies found between the primary and missing data analyses.

**Attrition bias.** As part of our examination of missing data, we will assess differences in baseline characteristics (e.g., clinic site, demographics, clinical values, medical history) by retention at each follow up time point. We will use two sample t-tests (or Wilcoxon rank sum tests) for continuous variables and  $\chi^2$  tests for categorical variables.

**Power.** The power calculation for this study was based on our prior nurse-led BP intervention, a meta-analysis of lipid-lowering medication adherence interventions, and baseline BP and cholesterol data from our clinic sites. Power estimates were derived empirically via simulation in SAS 9.4. Simulated data were generated based on estimates from prior studies, such that we assumed a mean SBP at baseline of 145 mmHg for both arms, with a reduction in the education control arm of 1 mmHg by 12 months. For the intervention arm, we evaluated effect sizes (differences from education control at 12 months) of 5-7 mmHg. We estimate that 15% of patients may drop out by the 12-month time point, and incorporated missing values into the simulated data based on a uniform pattern of 5% missing at 4 months, 10% at 8 months, and 15% at 12 months. The drop-out rate is consistent with prior interventions at our sites (80-88% retention at 12 months). We conservatively estimated variance components assuming a total standard deviation of 17 and a within-individual correlation of 0.4 among repeated SBP measurements. Similarly, for the secondary non-HDL outcome, we assumed a baseline value of 132 mg/dL with a standard deviation of 41 and a within-individual correlation of 0.7, and evaluated sample size needed over effect sizes ranging from 10-20 mg/dL. After generating 1,000 simulated datasets under these assumptions, we fit the LMMs described above to each and assessed the effect of interest using two-sided tests with a type I error rate of 0.05. Based on results, we will have >80% power to detect a 6 mmHg lower systolic BP and >90% power to detect a 15 mg/dL lower non-HDL cholesterol in the intervention arm vs. education control. Table 4 displays the sample sizes needed to detect a range of plausible ***clinically significant*** BP and non-HDL effects. A 6 mmHg improvement in systolic BP is associated with a ~20% decrease in ASCVD events, and a 15 mg/dL improvement in cholesterol is associated with ~10% decrease in clinical ASCVD events.

Pre-specified sub-group analyses of the primary and secondary outcomes will include clinic site, sex, and baseline ASCVD risk category (10-20%, >20% or prior ASCVD). For each category, we will examine the interactions with intervention arm and time. Generally, the modeling approach will mirror that described above

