**Part 2: Intervention and Process Evaluation**

**Aim 2: Evaluate the 12-month efficacy of a intervention to improve systolic blood pressure in Veterans with HIV.**

We will conduct an RCT of our intervention vs. education control among HIV Veterans on suppressive ART who have hypertension. Education control participants will receive general prevention education. The primary outcome is change in systolic BP and the secondary outcome will be change in non-HDL cholesterol. As participants conclude participation in the RCT the Aim 3 Process Evaluation will be conducted with select intervention participants. Relevant information from aim 2 for the process evaluation is highlighted in yellow.

**Setting:** This trial will be conducted at the same sites described earlier: Durham VA, Baltimore VA, Cleveland VA, and Atlanta VA

**Participants:** We will enroll 300 HIV+ Veterans on suppressive ART and poor hypertension control ( $n=25-125$  at each site). Inclusion and exclusion criteria is listed in section 5.4. We will include individuals who have **hyperlipidemia**, defined as non-HDL > National Lipid Association (NLA) target or on lipid-lowering medication based on the last 3 years. While 300 is our enrollment goal, we may consent and randomize up to 310, to account for site differences, withdrawals and the scheduling availability and preferences of Veteran participants.

**Baseline visit:** Participants will attend an in-person visit during which the informed process will be completed (see section 5.3 for informed consent procedures). Once the veteran has provided consent and enrolled in the study, the baseline visit will also consist of:

- Have in-office BP obtained by a trained research assistant using a standardized protocol. If blood pressure is identified by study staff as being high (>180/110), similar to prior trials, we will provide feedback to both the patient and his/her primary care provider. In terms of the Veterans' provider, we will use a developed CPRS template (requiring co-signature) and/or phone calls to notify them. If no action is taken, the study physician at each respective site will follow up with the patients' provider.
- Measurement of vitals: height, weight, waist circumference
- Have blood drawn at VA lab to measure lipid panel. If lipid panel has been completed in the past 28 days, will not need to repeat during baseline visit.

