**Subsequent visits: (4,8,12 months)**

- Have in-office BP obtained by a trained research assistant using a standardized protocol mentioned above.
- Complete health-related surveys (see full list of measures in section 5.5). Surveys may also be administered by telephone or by mail if Veteran is unable to complete the research visit in-person, but priority will be given to in-person survey administration.
- Measurement of vitals: weight, waist circumference
- Have blood drawn at VA lab to measure lipid panel. If lipid panel has been completed in the past 28 days, will not need to repeat during follow-up visit.

**Randomization:** Study statisticians will develop a 1:1 blocked randomization scheme, stratified by site and hyperlipidemia status. The project coordinator and research assistant will be blinded to the randomization schema and will randomize each subject using an automated randomization methods embedded in the study tracking software. Participants will be randomized to one of two groups:

- Education control group
- Intervention

[figure not shown]
**Education control group:** Participants assigned to the education group at baseline will receive usual care enhanced with general prevention education delivered by the research assistant in person at lab collection times (0, 4, 8, and 12 months). Providers will not be able to see research outcome assessment of BPs since these are not placed into CPRS.

We believe it would be unethical to use a usual care comparison group. The Education control group is receiving more than usual care: education material given at each visit, BP monitored and documented in CPRS, and providers notified if BP exceeds safety thresholds, requiring their co-signature.

**Intervention:** Participants assigned to the intervention will also complete in-person visits every 4 months, as listed above but will also have additional contact with our interventionist who may be either a nurse or pharmacist. The in-person visits will be identical to those in the education control group, but without the in-person education material. At their baseline visit, individuals enrolled in the intervention will be invited to consent and enroll in the VA Annie program, allowing them to submit home BP readings via text message before their intervention contacts. This is an existing VA program, but will not be required to participate in the intervention.

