We will assess mechanisms for missing data in this study. LMM implicitly accommodates missingness when the response is Missing At Random (MAR); that is, when missingness is due either to treatment, to prior outcome, or to other baseline covariates included in the LMM.

Our primary analysis will include all available study-collected data. We will first examine the amount of missingness at each timepoint for each of the two outcomes. We may impute missing values using multiple imputation procedures as described by Schafer. Each imputed dataset will be analyzed with the LMM model, and final parameter estimates and their standard errors will be calculated using Rubin's formula.

Notes on the protocol: The original protocol specified the following plan to fill in missing data (doing this process separately for each outcome):

1. Use all available study-reported data
2. If missing study-reported value, use the SBP or non-HDL cholesterol value if available in the EMR in a 2-month window from the target data for that time point.
3. If missing EMR-reported value, assess whether the outcome has >10% missing remaining
 - a. If yes, $\geq 10\%$ missing, use multiple imputation
 - b. If no, $<10\%$ missing, do not use multiple imputation, include only study- and EMR-reported values.

Updated plan: We will not plan to use EMR data for SBP due to concerns about the consistency of these measurements in different settings. For example, SBP may vary, with lower values observed in calmer settings. On the other hand, non-HDL cholesterol may be more consistent which could allow us to use EMR data. In addition, we will not use 10% as a strict threshold for imputation as it is unclear if this is 10% missing at each time point or overall. We will instead examine if characteristics vary by retention status at each time point. For example, there may be variables highly related to missingness but <10% missingness; in such a case, we may still want to impute missing values. Any baseline characteristic found to be associated with missingness at any time point will be included in the imputation model.

Attrition bias: As part of our examination of missing data, we will assess differences in baseline characteristics (e.g., clinic site, demographics, clinical values, medical history) by retention at each follow up time point. We will use two sample t-tests (or Wilcoxon rank sum tests) for continuous variables and chi-squared tests (or Fisher's exact test) for categorical variables.

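### The SAP's only stated rule for choosing imputation covariates is a low-power test against missed visits; a fixed set would be a cheap improvement to a sensitivity analysis.

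*Protocol*

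**What the plan says.** **Protocol, section 5.6.** The primary analysis is a linear mixed model (LMM) on all available study-collected data. The Missing data paragraph calls it valid when missingness depends on treatment, on earlier outcomes "or to other baseline covariates included in the LMM". Under Attrition bias, "we will assess differences in baseline characteristics (e.g., clinic site, demographics, clinical values, medical history) by retention at each follow up time point", using t or Wilcoxon tests and chi-squared tests. The Protocol does not link these comparisons to the imputation model.

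**SAP, Sensitivity Analysis/Missing Data.** The SAP repeats the comparisons and adds Fisher's exact test. Its updated plan drops the 10% trigger for imputation and looks instead at whether characteristics differ by retention. It then states: "Any baseline characteristic found to be associated with missingness at any time point will be included in the imputation model". The footnote to the Supplemental Table 2 shell reports the imputation covariates on that basis. Imputation is optional. Electronic medical record (EMR) values will not be used for SBP but may be used for non-HDL cholesterol.

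**SAP, Primary and Secondary Analyses.** Besides arm and visit, the SBP model contains site and hyperlipidemia. The update of 5/28/2025 removes hyperlipidemia from the non-HDL model. The update of 5/9/2025 replaces the random intercept with an unstructured covariance.

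Neither document gives a significance level for the retention comparisons, lists fixed imputation covariates, or includes a step that looks for predictors of the outcome.

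**The concern.** The LMM already uses arm, visit, all observed outcome values, site and, for SBP, hyperlipidemia. Normal-model imputation from the same variables gives essentially the same answer. For SBP, with EMR values set aside, imputation can add information only through further baseline variables, so the rule that admits them determines what the sensitivity analysis can show. For non-HDL cholesterol, EMR values may add information as well.

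The rule has two weaknesses. It relies on tests with few missing participants, so a moderate predictor of dropout can easily go unflagged. It also looks at one relation only. Omitting a baseline variable causes bias when the variable is related to both missingness and outcome. A good predictor of SBP with a modest, non-significant link to dropout is therefore worth including, and nothing in the rule brings it in. A variable that predicts the outcome but not missingness would add precision only.

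At stake is how agreement is read. If imputation and LMM give the same result, it may be reported as robustness when the screen simply admitted little that was new.

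**Working it through.** **Inputs**
- Sample size: "We will enroll 300 HIV+ Veterans on suppressive ART and poor hypertension control" (Protocol 5.1, Aim 2; up to 310 may be randomized).
- Allocation: "Study statisticians will develop a 1:1 blocked randomization scheme, stratified by site and hyperlipidemia status".
- Missingness: "uniform pattern of 5% missing at 4 months, 10% at 8 months, and 15% at 12 months" (Protocol 5.6, Power), so 0.05 × 300 = 15, 0.10 × 300 = 30 and 0.15 × 300 = 45. Prior studies had "80-88% retention at 12 months", which gives 36 to 60 missing at month 12.
- SBP: SD 17 mmHg, within-person correlation 0.4, target difference 6 mmHg.
- Test level: the power simulations "assessed the effect of interest using two-sided tests with a type I error rate of 0.05". The retention comparisons have no stated level; I assume 0.05 two-sided.

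**1. The plan's own figure.** Generalized least squares for the stated model (common baseline, compound symmetry, monotone 5/10/15% dropout, n = 300) gives a standard error of 1.94 mmHg for the 12-month difference. Power = Φ(6/1.94 − 1.96) = 87%, consistent with the stated figure above 80%. The missingness inputs are therefore read correctly.

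**2. Screen, continuous characteristic.** For a standardized difference d between missing and retained participants, power ≈ Φ(d/√(1/m + 1/(300 − m)) − 1.96). At m = 45 the root is √(1/45 + 1/255) = 0.162. For d = 0.3: Φ(0.3/0.162 − 1.96) ≈ 46%. The d needed for 80% power is (1.96 + 0.84) × 0.162 = 0.45 at month 12; the same formula gives 0.54 at month 8 and 0.74 at month 4.

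| d | Month 12 | Any visit (simulated) |
|---|---|---|
| 0.2 | 23% | 31% |
| 0.3 | 46% | 52% |
| 0.4 | 69% | 74% |
| 0.5 | 87% | 89% |

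At d = 0.3, month-12 power runs from 39% (36 missing) to 55% (60 missing). With 45 missing, a level of 0.10 or 0.20 gives 58% or 72%.

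**3. Screen, binary characteristic.** Simulated chi-squared tests, 30% prevalence, monotone dropout:

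| Effect on dropout | Month 4 | Month 8 | Month 12 | Any visit |
|---|---|---|---|---|
| None | 5% | 5% | 5% | 11% |
| 1.5-fold | 14% | 23% | 32% | 40% |
| 2-fold | 30% | 52% | 71% | 74–76% |
| 2.5-fold, both arms | 47% | 76% | 92% | 93% |
| 2.5-fold, one arm only | 17% | 29% | 41% | 48% |

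**4. Size of the bias from one omitted factor.** Take a 30%-prevalence factor that raises dropout 2.5-fold in one arm. Month-12 missingness without the factor is 0.15/(0.7 + 0.3 × 2.5) = 10.3%, and with it 25.9%. Prevalence among those observed is 0.3 × (1 − 0.259)/0.85 = 0.262, a shift of 0.0383.
- If the factor affects SBP only at month 12, the bias is 0.0383 × 6 = 0.23 mmHg for a 6 mmHg factor and 0.0383 × 10 = 0.38 mmHg for a 10 mmHg factor.
- If it affects SBP at every visit, the LMM recovers part of it from earlier readings. Large-sample simulation of the fitted model gives about 0.10 and 0.15 mmHg.

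If dropout depends on the factor alike in both arms, the shift largely cancels in the difference.

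**The case against.** The case on the other side is substantial, and much of it stands.

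- **Location.** The Protocol's attrition paragraph is descriptive and contains no error. The rule is in the SAP alone.
- **Silence is not exclusion.** A reader might infer that the SAP bars every covariate that is not flagged, or refuses predictors of SBP. It does neither: it says what goes in and is silent on the rest. Outcome predictors are unspecified. The choice is still left until after the data are seen.
- **Strong predictors are mostly found.** The rule applies at any visit, which raises detection. A reader might infer that real dropout predictors are generally missed. That fits factors of about 1.5-fold or 0.3 SD. It does not fit a 2.5-fold factor acting in both arms (93%). The factors missed tend to be those that bias least.
- **The check is unlikely to be empty.** The Table 1 shell has 19 variables besides site and hyperlipidemia. If none were related to dropout and all were independent, the chance that none is flagged is 0.89^19 ≈ 11%. Chance flags, however, bring in noise and do not show that useful variables were admitted.
- **Non-HDL differs.** Possible EMR values are new outcome data, so the covariate rule is not the only source of information there.
- **Materiality.** The bias is a fraction of a millimetre of mercury, and the analysis is optional.

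What remains is that the only stated rule has low power for moderate predictors, takes no account of the outcome, and can be replaced at almost no cost.

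**Conclusion.** The point holds as a minor, inexpensive improvement to the SAP's missing-data section. Selection by observed association with missingness flags a 1.5-fold dropout factor about 40% of the time, a 0.3 SD difference about 52% and an unrelated variable about 11%, counting any of the three visits. For SBP, agreement between imputation and LMM would therefore be weaker evidence of robustness than it looks. For non-HDL cholesterol the same weakness applies in part.

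The likely bias from one omitted factor is about 0.1 to 0.15 mmHg if it acts at all visits, and up to 0.23 to 0.38 mmHg if it acts only at month 12, against a 6 mmHg target. A reader might infer that the primary result is compromised or that several omitted factors would add up to something large. The documents support neither: the primary estimate does not use the imputation model, and separate omissions may cancel.

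These figures rest on the planned 5/10/15% missingness, an assumed 0.05 level, and illustrative values for prevalence, dropout effect and SBP effect that the documents do not give.

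**What to change.** In the SAP's updated missing-data plan, replace the test-based rule with an imputation set fixed in advance and used whatever the retention comparisons show:

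- arm, and the outcome at all four visits;
- site and hyperlipidemia, the latter also when imputing non-HDL cholesterol, although that LMM omits it;
- Table 1 baseline variables that plausibly predict the outcome or retention, for example age, sex, race, smoking, ASCVD risk, education, employment, financial status, housing or food insecurity, rurality, and the chaos and loneliness scores.

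Add any further variable that the retention comparisons flag, and otherwise report those comparisons as description. Change the Supplemental Table 2 footnote to list the fixed set and any additions. The Protocol's attrition paragraph can stay as it is.

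The cost is a few lines of SAP text and slightly longer imputation code. All the variables are already collected. The downside is a somewhat larger imputation model, manageable with 300 participants.
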